4.2 Phase II

4.2.1 Inclusion Criteria

- 4.2.1.1** Patients must have cytologically or histologically confirmed ES-SCLC and must not have progressed after first line platinum-based chemotherapy regimen before randomization.
- 4.2.1.2** Patients with tumor tissue uptake during NETSPOT[®] PET that is equal to or higher than that in normal hepatic tissue (grade ≥ 2) will be eligible. It is recommended that NETSPOT[®] PET be obtained before initiation of chemotherapy, but NETSPOT[®] PET obtained during or after completion of chemotherapy could be used for screening purpose.
- 4.2.1.3** Toxicities of prior therapy must be resolved to grade 1 or less as per Common Terminology Criteria for Adverse Events (CTCAE) version 4.03 with the exception of alopecia and grade 2, prior platinum-therapy related neuropathy.
- 4.2.1.4** Prior radiotherapy or radiosurgery (including prophylactic cranial radiation and/or thoracic radiation) must have been completed at least 2 weeks prior to randomization.
- 4.2.1.5** For patients who do not receive radiotherapy after chemotherapy, the randomization must occur within 6 weeks of the last chemotherapy cycle. The study treatment must start within 2 weeks from randomization and no less than 2 weeks from last chemotherapy dose. For patients who receive radiotherapy (including prophylactic cranial radiation and/or thoracic radiation) after chemotherapy, the randomization must occur at least 8 weeks after completion of radiation therapy but within 12 weeks after completion of radiation therapy.
- 4.2.1.6** ECOG performance status of 0-1.

- 4.2.1.7** Adequate organ and bone marrow function (hemoglobin > 9 g/dL; absolute neutrophil count > $1.5 \times 10^9/L$; platelet counts > $100 \times 10^9/L$; serum bilirubin < 2 x ULN (except subjects with Gilbert Syndrome who must have total bilirubin < 3.0 mg/dL); alanine aminotransferase (ALT) and aspartate aminotransferase (AST) < 2.5 x ULN or < 5 x ULN if liver metastases; calculated creatinine clearance > 50 mL/min).
- 4.2.1.8** Life expectancy of at least 3 months.
- 4.2.1.9** Age > 18 years.

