5.1.2 Phase II

The phase II portion will consist of patients with ES-SCLC who completed platinum based standard first-line chemotherapy (e.g. 4-6 cycles of platinum plus etoposide or irinotecan) without disease progression (responders plus stable disease) at the time of initiation of the combination therapy with $^{177}\text{Lu-DOTA}^0\text{-Tyr}^3\text{-Octreotate}$ and nivolumab. Eligible patients will then be randomly allocated in two arms: one will be treated with the combination of $^{177}\text{Lu-DOTA}^0\text{-Tyr}^3\text{-}$

Octreotate and nivolumab, and the other arm will continue be followed (observation) after completion the standard chemotherapy treatment.

Randomization:

Patients who do not receive radiotherapy after chemotherapy

- The randomization must occur within 6 weeks of the last chemotherapy cycle.
- The study treatment must start within 2 weeks from randomization, but no less than 2 weeks from last dose of chemotherapy.

Patients who receive radiotherapy (including prophylactic cranial radiation and/or thoracic radiation) after chemotherapy

- Randomization must occur at least 8 weeks after completion of radiation therapy but within 12 weeks after completion of radiation therapy.

Randomization process:

- OnCore will be used as statistical center and the randomization algorithm will be developed by the study biostatistician.
- The project management department will be the first point of contact for assessment through email.

Courses are defined as 56 days of dosing. Nivolumab will be given until progressive disease, patient withdrawal, or toxicities. For patients randomized to the observation group, cross-over at the time of disease progression will be allowed, since the primary endpoint is PFS and not OS.

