5.2.2 Nivolumab

Nivolumab will be administered once every 2 weeks until disease progression, patient withdrawal or toxicities. Nivolumab is administered intravenously and is administered first in combination studies. Wait 30 minutes before the next compound is administered (regardless of route of administration). Administer the infusion over 30 minutes (+/- 5 minutes) through an intravenous line containing a sterile, non-pyrogenic, low protein binding in-line filter (polyethersulfone with pore size of 0.2 micrometer to 1.2 micrometer). Do not coadminister other drugs through the same intravenous line. Nivolumab infusions are compatible with PVC or polyolefin containers and infusion sets, and glass bottles. Flush the intravenous line at end of infusion with appropriate amount of diluent (15-20 ml) to ensure that the total dose is administered. Administration of nivolumab may be given one day earlier or delayed up to 1 week due to holidays, inclement weather, conflicts, or similar reasons. The timing of subsequent administrations is then adjusted to maintain a 14 days-interval.

5.3 Dose Delays/Dose Modifications and Management of Toxicities Associated with ¹⁷⁷Lu-DOTA⁰-Tyr³-Octreotate and nivolumab

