6.2 Procedures During Treatment

Patients receiving study treatment will be followed every 2 weeks and the following will be done (unless otherwise indicated).

- History and physical exam (\pm 3 days).
- Laboratory evaluation (\pm 3 days): Hematologic profile (CBC with differential). Biochemical profile. Does not need to repeat for C1D1 if performed within 7 days.
- Thyroid function testing will be done every cycle on day 1 (\pm 3 days) and day 29 (\pm 3 days) for subjects receiving nivolumab. Does not need to repeat on C1D1.
- Tumor imaging will be performed every 8 weeks (\pm 7 days).
- NETSPOT[®] PET scan on cycle 2 day 1 (\pm 3 days) to assess the metabolic response.
- Serum or urine beta-hCG for female patients of childbearing age within 24 hours prior to the administration of ¹⁷⁷Lu-DOTA⁰-Tyr³-Octreotate.

Patients randomized to observation will be followed every 4 weeks and the following will be done.

- History and physical exam (\pm 3 days).
- Laboratory evaluation (\pm 3 days): Hematologic and biochemical profile. Laboratory evaluation can be performed within 3 days prior to clinic visit.
- Tumor imaging will be performed every 8 weeks (\pm 7 days).

After 30 days (\pm 7 days) from treatment termination, the following will be obtained if the patient is available:

- History and physical exam.
- Laboratory evaluation: Hematologic and biochemical profile. Thyroid function testing.

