7.1.6 Progression-Free Survival

PFS is defined as the duration of time from randomization to time of progression or death, whichever occurs first.

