Amylase	X										
Lipase	X										
HBsAg ^e	X										
anti-HCV ^e	X										
anti-HIV ^e	X										
Pregnancy test ^f	X		X ^f				X ^f				
Tumor biopsy	X ^g	Optional at the time of progression									
Nivolumab ^h		X	X	X	X	X	X	X	X		
¹⁷⁷ Lu-DOTA ⁰ -Tyr ³ -Octreotate			X				X ^h				
Long-term follow up including survival											X ⁱ

- a: Initial tumor assessment will be performed at C2 D1 (\pm 7 days) and every 8 weeks (\pm 7 days) thereafter.
 - b: Refer to section 6.1 for details
 - c: On treatment Netspot only on cycle 2 day 1 (\pm 3 days)
 - d: Thyroid function testing will be done every cycle on day 1 (\pm 3 days) and day 29 (\pm 3 days). Does not need to repeat on C1D1.
 - e: Within three months prior to starting study treatment
 - f: Only for women of child bearing potential (WOCBP). Within 24 hours prior to the administration of $^{177}\text{Lu-DOTA}^0\text{-Tyr}^3\text{-Octreotate}$.
 - g: Optional. Utilization of archival tissue will be allowed.
 - h: May be given one day earlier or delayed up to 1 week. $^{177}\text{Lu-DOTA}^0\text{-Tyr}^3\text{-Octreotate}$ will only be given for 4 cycles.
 - i: Annually for two years
 - j: C1D1 laboratory tests do not need to be repeated if the screening laboratory tests were done within 7 days from C1D1.
- * Refer to section 6.2 for details about time windows within which each procedure should be performed.

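### Tumor scans are not tied to randomization, none is scheduled after stopping before progression, and PFS has no censoring rule, so the primary comparison can be biased

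*Combined protocol and SAP*

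**What the plan says.** - **Time origin.** Section 7.1.6: "PFS is defined as the duration of time from randomization to time of progression or death, whichever occurs first". Section 11.3 repeats this.
- **Combination scans.** Appendix D, footnote a: "Initial tumor assessment will be performed at C2 D1" (±7 days), then 8-weekly. A cycle is 56 days, so this is 8 weeks after first dose. For patients without radiotherapy after chemotherapy, Section 4.2.1.5 says "The study treatment must start within 2 weeks from randomization and no less than 2 weeks from last chemotherapy dose". For those with radiotherapy, Section 5.1.2 says only "Randomization must occur at least 8 weeks after completion of radiation therapy but within 12 weeks after completion of radiation therapy" and sets no limit from randomization to first dose. A nivolumab dose may be up to a week late, after which "The timing of subsequent administrations is then adjusted to maintain a 14 days-interval" (Section 5.2.2), so C2D1 can move further.
- **Observation scans.** Section 6.2: "Patients randomized to observation will be followed every 4 weeks and the following will be done", with "Tumor imaging will be performed every 8 weeks" (±7 days) and no start date. The calendar has treatment-cycle columns only.
- **Baseline.** Sections 6.1 and 7.1.3 count the 4-week and 28-day windows back from the start of study drugs or treatment.
- **After stopping.** The combination arm's 8-weekly imaging is listed under "Patients receiving study treatment will be followed every 2 weeks and the following will be done". The 30-day visit, the EOT and Follow-up columns and Section 6.3 list no tumor imaging. Follow-up is yearly, by visit or telephone; a progression date is recorded, but no scan is scheduled to establish it.
- **Censoring.** Section 11.3 gives a rule for OS and none for PFS.

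**The concern.** Progression is usually recorded at the scan that finds it, not when it happens. If one arm is scanned systematically later after randomization, its events are recorded later even when true PFS is identical. Log-rank and Cox work on the order of event times, so a small shift can put a whole cluster of one arm's events ahead of the other's. This trial is exposed because the assumed control median is about one scan interval and the analysis rests on 40 events.

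Stopping adds a second route. A combination patient who stops before progression leaves the only scan schedule that applies to that arm. If such patients are censored at their last scan and stopping is linked to approaching progression, events are lost from one arm only. With no PFS censoring rule, the handling would be chosen after an open-label trial has produced its data.

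**Working it through.** **The plan's own size (Section 11.2).** Two-sided 0.05, 80% power, HR = 2/5 = 0.4; 1:1 allocation is assumed because no ratio is stated.
- Schoenfeld events = 4(1.960 + 0.842)² / (ln 0.4)² = 31.4 / 0.840 = 37.4, so 38 against the stated 40. Power at 40 events is 82.6%.
- 44 / 0.85 = 51.8, so 52, as stated.

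The sample size is not in question.

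**Why the first scan dominates.** Two months = 2 × 30.44 / 7 = 8.7 weeks. Under an exponential model, P(progression by week 8) = 1 − 2^(−8/8.7) = 47%. By week 10 it is 1 − 2^(−10/8.7) = 55%. With scans at week 8 in one arm and week 10 in the other, about half of each arm's events fall in two separate clusters, one always ahead of the other.

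**Null simulation.** 26 per arm, both medians 2 months, accrual 3.5 per month, analysis at the 40th event. Scan k is at 8k weeks + offset + uniform(−1, 1) week; the event is recorded at the first scan on or after progression. Tie-corrected log-rank, Efron Cox HR (geometric mean), 4,000 trials per scenario. False positives are those favouring the combination (nominal 2.5%); Monte Carlo SE is about 0.25 points at 2.6% and 0.45 at 8.8%. Except in the aligned and same-offset rows, observation scans run from randomization and combination scans from first dose.

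| Scenario | HR | False positives |
|---|---|---|
| Scans aligned | 1.00 | 2.6% |
| Same 0–2 week offset in both arms | 1.00 | 3.0% |
| Combination lag 0–2 weeks | 0.83 | 8.8% |
| Combination lag fixed at 2 weeks | 0.76 | 14–15% |
| 0–2 week lag, 15% / 30% of events dated exactly | 0.87 / 0.90 | 6.7% / 6.1% |
| 0–2 week lag, 25% / 50% / 75% of progressions found at the next clinic visit (2-weekly v 4-weekly) | 0.89 / 0.97 / 1.04 | 6.0% / 3.2% / 1.5% |

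Repeat simulations gave HR 0.82–0.83 and 7.8–9.9% for the 0–2 week lag, and HR 0.75–0.76 and 12.7–14.9% for the fixed lag.

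**Under the design effect** (2 v 5 months), a 0–2 week lag moves the HR from 0.40 to 0.35, or to 0.36 / 0.38 with 15% / 30% exact dating.

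**Reverse case** (22 per arm, 1,000 trials, observation scanned 2 weeks later): null HR 1.29. At true HR 0.4 the estimate is 0.47 and power is 64%, against 80% when aligned.

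**Stopping** (scans aligned; 10 / 20 / 30% of the combination arm censored at the last scan; rates assumed, since the documents give none).
- Unrelated to progression: HR 1.00 / 1.04 / 1.06.
- Before an unseen progression: HR 0.95 / 0.89 / 0.81; false positives 4.3 / 5.4 / 8.7%.

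**Can analysis repair it?** (2,000 null trials; the Weibull interval-censored model is correctly specified here.)
- 0–2 week lag: interval-censored on actual scan dates HR 1.00, 2.5%; events assigned to nominal visits 1.08, 1.8%.
- Fixed 2-week lag: interval-censored 0.99, 2.9%; nominal visits 1.14, 0.5%, an overcorrection.

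**The case against.** The strongest reply is that the asymmetry is assumed. Section 6.2 gives both arms the same 8-week interval, and nothing says observation scans run from randomization. The documents are silent rather than contradictory, and a shared offset gives no bias. This stands as a limit on direction and size. It does not remove the gap: the one written anchor depends on dosing and cannot apply to the observation arm.

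Second, mitigating factors act together. Deaths count as PFS events, and this disease often declares itself by symptoms between scans. With a 0–2 week lag, 15% exact dating and 25% of progressions found at visits, the HR is 0.92 with 4.1% false positives; at 50% found at visits it is 0.98 with 2.9%. These shares are assumptions too, but they show that 8.8% and 14–15% are upper illustrations. The fixed 2-week lag also needs every patient to start on the last permitted day.

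Third, drift is limited. Only the first scan is tied to C2D1, and for radiotherapy patients the 28-day baseline window indirectly limits a late start.

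Fourth, complete stopping may be uncommon, since Sections 5.3.1 and 5.3.3 let one drug continue while the other is held. Section 7.1.4.3 does ask that progression be documented after discontinuation, but only for symptomatic deterioration and with no interval. The related-stopping scenario also leaves out later deaths, which would count as events, so it too is at the high end.

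**Conclusion.** The concern holds, as something that should be fixed. No section supplies a randomization anchor for scans or baseline, a scan schedule after stopping before progression, or a PFS censoring rule.

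If observation scans run from randomization and combination scans from first dose, the permitted 0–2 week gap alone can move a null HR to about 0.83 and raise false positives for the combination to about 9%. Realistic dilution brings this to roughly 3–7%, and it can slightly reverse. If observation is scanned later, the trial loses power instead. Censoring stoppers at the last scan is near neutral only if stopping is unrelated to progression. The plan does not settle which case applies.

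Confidence in the gap is high; confidence in the size and direction of bias is only moderate. The figures assume 1:1 allocation, exponential PFS, and shares for lag, stopping, exact dating and visit detection that the documents do not give.

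**What to change.** 1. **Sections 6.2 and 6.3 and Appendix D.** In both arms, schedule tumor imaging at weeks 8, 16, 24 and so on (±7 days) from randomization, regardless of treatment start, dose delay or stopping, until RECIST progression, death or withdrawal of consent. Add an observation-arm column to the calendar.
2. **Sections 6.1 and 7.1.3.** Anchor the 28-day baseline scan window to randomization in both arms.
3. **Section 11.3.** State a PFS censoring rule, for example at the last adequate tumor assessment, to be used together with continued scanning after stopping.
4. **Section 11.3.** Add one sensitivity analysis: interval-censored PFS on actual scan dates. Assigning events to nominal visits is suitable only once both arms share the schedule.

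The cost is protocol and calendar wording, a few CTs at the interval already planned for patients who stop early without progression, and one extra analysis. The 40-event design is unaffected: with a common scan origin (22 per arm), simulated power at HR 0.4 is 80.2%.

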6.3 Follow-up

Patients will be followed either with clinic visits or phone interviews yearly for two years.

Patients removed from treatment for unacceptable adverse event(s) will be followed clinically until

resolution or stabilization of the adverse event, and then via clinic visits or phone interviews yearly for two years.

The following information will be collected:

- Date of follow up
- Is patient dead or alive?
- If dead, document exact date of death.
- Further treatment(s), if any
- Document date of disease progression
- Long-term myelosuppression, myelodysplasia, and occurrence of secondary malignancies.

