8.3 Reporting Requirements for Adverse Events

Participating investigators (all sites) must report all serious adverse events to the Sponsor-Investigator within **24 hours** of discovery or notification of the event. The participating investigator must also provide follow-up information on the SAE until final resolution. The Sponsor-Investigator can be contacted at [name], E-mail: [contact], [contact] with CC to [contact] and CC to sub-investigator [name], E-mail: [contact].

The Sponsor-Investigator will review the SAE and report the event to the FDA, external collaborator(s), IND manufacturer, and IRB as applicable as described below.

It is the Sponsor-Investigator's responsibility (e.g. lead site PI) to ensure that all serious adverse events that occur on the study (e.g. all SAEs that occur at each enrolling institution) are reported to all participating sites.

*After informed consent has been obtained but prior to initiation of study treatment, only serious adverse events caused by a protocol-mandated intervention (e.g., invasive procedures such as biopsies) should be reported.

**After initiation of study treatment, all adverse events will be reported until 30 days after the last dose of study treatment or last observation follow-up visit or until initiation of new systemic anti-cancer therapy, whichever occurs first, and serious adverse events will continue to be reported until 90 days after the last dose of study treatment or last observation follow-up visit or until initiation of new systemic anti-cancer therapy, whichever occurs first.

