Appendix C. ECOG Performance Status Score

ECOG Performance Status Scale		Karnofsky Performance Scale	
Grade	Descriptions	Percent	Description
0	Normal activity. Fully active, able to carry on all pre-disease performance without restriction.	100	Normal, no complaints, no evidence of disease.
		90	Able to carry on normal activity; minor signs or symptoms of disease.
1	Symptoms, but ambulatory. Restricted in physically strenuous activity, but ambulatory and able to carry out work of a light or sedentary nature (e.g., light housework, office work).	80	Normal activity with effort; some signs or symptoms of disease.
		70	Cares for self, unable to carry on normal activity or to do active work.
2	In bed <50% of the time. Ambulatory and capable of all self-care, but unable to carry out any work activities. Up and about more than 50% of waking hours.	60	Requires occasional assistance, but is able to care for most of his/her needs.
		50	Requires considerable assistance and frequent medical care.
3	In bed >50% of the time. Capable of only limited self-care, confined to bed or chair more than 50% of waking hours.	40	Disabled, requires special care and assistance.
		30	Severely disabled, hospitalization indicated. Death not imminent.
4	100% bedridden. Completely disabled. Cannot carry on any self-care. Totally confined to bed or chair.	20	Very sick, hospitalization indicated. Death not imminent.
		10	Moribund, fatal processes progressing rapidly.
5	Dead.	0	Dead.

ASSESSMENT/EVENT	Screening	Treatment Period*									
		C1	C1	C1	C1	C2 and beyond	C2 and beyond	C2 and beyond	C2 and beyond	EOT	Follow-up
Study Visit		D1	D15	D29	D43	D1	D15	D29	D43		
Informed consent	X										
ECOG PS	X	X	X	X	X	X	X	X	X	X	
History and physical examination	X	X	X	X	X	X	X	X	X	X	
Adverse event assessments		X	X	X	X	X	X	X	X	X	
Vital Signs	X	X	X	X	X	X	X	X	X	X	
Height and weight	X										
Concomitant Medications Collection	X	X	X	X	X	X	X	X	X	X	
12 Lead ECG	X										
Tumor imaging ^a	X					X					
Brain imaging (MRI or CT)	X	To be performed as clinically indicated at the discretion of the investigator									
FDG-PET	X	To be performed as clinically indicated at the discretion of the investigator									
NETSPOT PET ^b	X					X ^c					
CBC with differential	X	X ^j	X	X	X	X	X	X	X	X	
PT/aPTT	X										
Comprehensive Metabolic Panel	X	X ^j	X	X	X	X	X	X	X	X	
Thyroid function test ^d	X			X		X		X		X	
LDH	X	X ^j	X	X	X	X	X	X	X	X	
Magnesium	X	X ^j	X	X	X	X	X	X	X	X	
Phosphorus	X	X ^j	X	X	X	X	X	X	X	X	

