The collection of nonserious AE information should begin at initiation of study drug. All nonserious adverse events (not only those deemed to be treatment-related) should be collected continuously during the treatment period and for a minimum of 100 days following the last dose of study treatment. Nonserious AEs should be followed to resolution or stabilization, or reported as SAEs if they become serious. Follow-up is also required for nonserious AEs that cause interruption or discontinuation of study drug and for those present at the end of study treatment as appropriate.

Laboratory Test Abnormalities

All laboratory test results captured as part of the study should be recorded following institutional procedures. Test results that constitute SAEs should be documented and reported as such. The following laboratory abnormalities should be documented and reported appropriately:

- Any laboratory test result that is clinically significant or meets the definition of an SAE
- Any laboratory abnormality that required the subject to have study drug discontinued or interrupted
- Any laboratory abnormality that required the subject to receive specific corrective therapy.

Pregnancy

If, following initiation of the investigational product, it is subsequently discovered that a study subject is pregnant or may have been pregnant at the time of investigational product exposure, including during at least 6 half lives after product administration, the investigational product will be permanently discontinued in an appropriate manner (e.g. dose tapering if necessary for subject safety). The investigator must immediately notify Worldwide Safety @BMS of this event via the Pregnancy Surveillance Form in accordance with SAE reporting procedures. Follow-up information regarding the course of the pregnancy, including perinatal and neonatal outcome and, where applicable, offspring information must be reported on the Pregnancy Surveillance Form

[provided upon request from BMS]. Any pregnancy that occurs in a female partner of a male study participant should be reported to BMS. Information on this pregnancy will be collected on the Pregnancy Surveillance Form.

Overdose

An overdose is defined as the accidental or intentional administration of any dose of a product that is considered both excessive and medically important. All occurrences of overdose must be reported as an SAE.

Other Safety Considerations

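### SAEs are reportable for 90 days after the last dose, but no scheduled contact asks about new ones between the visit about 30 days after treatment ends and the yearly follow-up; the AE windows also conflict

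*Combined protocol and SAP*

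**What the plan says.** **Reporting windows.** Section 8.3 states that "serious adverse events will continue to be reported until 90 days after the last dose of study treatment or last observation follow-up visit", and closes the window sooner if new systemic anti-cancer therapy begins. The same sentence gives 30 days for all adverse events, with the same early stop, and Section 8.1.1 also gives 30 days. Appendix E asks for non-serious events "for a minimum of 100 days following the last dose of study treatment", with no stop at new therapy. It also sets 30 days after dosing ends for SAE reports to the nivolumab manufacturer, plus any later SAE believed to be related.

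**Scheduled contacts.** In the Study Calendar the row "Adverse event assessments" is marked at every treatment visit and at EOT, and is blank under Follow-up. The calendar does not date EOT. Section 6.2 describes one post-treatment visit, 30 ± 7 days "from treatment termination, the following will be obtained if the patient is available"; its content is history, physical examination, laboratory tests and thyroid tests. Section 6.3 then says: "Patients will be followed either with clinic visits or phone interviews yearly for two years". The calendar footnote agrees: "i: Annually for two years".

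**Content of the yearly contact.** Sections 5.7 and 6.3 list vital status and date of death, further treatment and date of progression. Section 6.3 adds "Long-term myelosuppression, myelodysplasia, and occurrence of secondary malignancies". Neither list has a general AE or SAE item.

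**The concern.** The plan sets a 90-day SAE obligation, but its calendar has no contact that could meet it after the visit about 30 days after treatment ends. An SAE on day 60, say, enters the database only if someone volunteers it. If the yearly contact is run from its listed items, it does not ask.

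Safety of the combination is a secondary objective of both phases (Section 3.3.1), and Section 5.1.1.2 notes that the combination had not been tested in clinical trials. The plan itself expects immune-related toxicity to run beyond a month: Table 6 has steroid tapers of a month or more, and one of its footnotes refers to 12 weeks after the last dose. A post-treatment SAE rate that depends on volunteered reports is likely to be too low, by an amount the trial could not estimate. The conflicting windows add a second problem, because sites following different sections would collect different data.

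**Working it through.** The plan gives no figure to reproduce. The check compares visit timing with the windows.

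**Inputs**
- W, the window after the last dose: 90 days for SAEs (Section 8.3); 100 days for non-serious AEs (Appendix E); 30 days for AEs (Sections 8.1.1 and 8.3).
- V, the day of the post-treatment visit, counted from treatment termination: 30 ± 7, so 23, 30 or 37 (Section 6.2). Treating this visit as the calendar's EOT is an inference from matching content.
- D, days from last dose to termination: not stated. I take 0 and 14. The 14 arises when treatment stops at a scan: the last nivolumab dose of a cycle is on D43 and the next scan is on D1 of the following 56-day cycle (day 57), and 57 − 43 = 14.

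**Formula.** Days with no scheduled enquiry = max(0, W − (V + D)); share = that number / W.

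| Window W | D | Visit at V = 23 | V = 30 | V = 37 |
|---|---|---|---|---|
| 90 (SAE) | 0 | 67 (74%) | 60 (67%) | 53 (59%) |
| 90 (SAE) | 14 | 53 (59%) | 46 (51%) | 39 (43%) |
| 100 (non-serious, Appendix E) | 0 | 77 (77%) | 70 (70%) | 63 (63%) |
| 100 (non-serious, Appendix E) | 14 | 63 (63%) | 56 (56%) | 49 (49%) |
| 30 (AE, 8.1.1 and 8.3) | 0 | 7 (23%) | 0 | 0 |
| 30 (AE, 8.1.1 and 8.3) | 14 | 0 | 0 | 0 |

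For the 90-day SAE window the range is 39 to 67 days, or 43 to 74%. A termination date more than 14 days after the last dose shortens the gap day for day.

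**If the 30-day visit is missed.** The last enquiry is then the last treatment-period visit, on day 0 or day 14 after the last dose. The gap is 90 − 0 = 90 or 90 − 14 = 76 days. The same result follows if EOT means the day treatment stops, because the Section 6.2 list for the 30-day visit names no AE assessment.

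**Next contact.** If the first yearly contact falls near day 365 after the last dose (assumption), it comes 365 − 90 = 275 days after the SAE window closes.

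**Observation arm.** Section 8.3 counts 90 days from the last observation visit. Section 6.2 ties the 30-day visit to treatment termination, so it is unclear whether observation patients have one at all.

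**The case against.** Several points on the other side stand.

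- **Shorter windows are also in the plan.** If 30 days governs non-serious AEs, the post-treatment visit covers that window almost fully (at most 7 days uncovered). A reader might infer that a gap exists whichever window governs. The documents do not support that: the 100-day gap is conditional on Appendix E, and only the 90-day SAE gap stands without that condition.
- **The window can close early.** Section 8.3 stops at new systemic anti-cancer therapy. Many patients will progress, and some will start such therapy soon. For a patient who starts it on day t after the last dose, the gap is max(0, t − (V + D)), which may be zero. So 39 to 67 days applies to patients who start none. The documents do not say how many that is.
- **Known events are followed.** Patients removed for toxicity are followed until that event resolves or stabilises (Sections 5.7 and 6.3). Section 8.1.1 follows all AEs to resolution, and Appendix E follows those present at end of treatment. SAEs are due within 24 hours of discovery or notification, and the yearly contact records deaths and late marrow effects. A reader might infer that late events are never captured; that is too strong. What is missing is a scheduled search for new events.
- **One late call looks backwards.** It improves completeness of the data more than early detection of a toxicity.

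None of this supplies a contact that asks about new SAEs between the visit about 30 days after treatment ends and the end of the 90-day window.

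**Conclusion.** The mismatch is real and should be corrected. For treated patients who start no new systemic therapy, 39 to 67 of the 90 SAE days (43 to 74%) have no scheduled enquiry about new SAEs, and the post-treatment SAE rate therefore rests on passive reporting. This assumes that EOT is the Section 6.2 visit, that the visit takes place, and that termination falls 0 to 14 days after the last dose.

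Two stronger readings do not follow. It is not secure that most of the SAE window is uncovered, since the share falls to 43% when treatment ends at a scan and the visit is late. Nor can the gap be turned into a number of missed SAEs: the documents give neither a post-treatment SAE rate nor the share that would be volunteered.

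Separately, the 30-, 90- and 100-day statements conflict and must be reconciled, whatever view is taken of the gap.

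**What to change.** 1. Reconcile the windows in Sections 8.1.1 and 8.3 and Appendix E, so that one window is stated for non-serious AEs and one for SAEs. State the reference date (last dose or termination) and whether new systemic therapy ends each window. Give the manufacturer-reporting window separately if it is meant to differ.
2. Then add to Section 6.2 and Appendix D one phone or clinic contact, with an AE/SAE item, at the end of the governing window, covering at least the 90-day SAE window. Include all treated patients, cross-over patients among them, and observation patients at the matching time after their last observation visit.
3. Date EOT in the calendar, and let a phone contact replace a missed 30-day visit.

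The cost is one call and one CRF line per patient. Reported toxicity will be slightly higher because ascertainment is better. No extra patients or scans are needed.
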